1. SYNOPSIS

Study Objective	To assess and compare tissue aggregation and visualization of two (2) Hyaluronic Acid fillers via ultrasound
Methodology	Randomized, split-face, subject-blinded, comparative study
Number of Subjects at the end	15 subjects to complete
Study duration	24 weeks
Test products	Restylane Contour Juvéderm Voluma
Conditions of use	Per on-label instruction
Study visits	Day 0, week 4, and week 24
Specific Inclusion Criteria:	
 ○ Demographics and study skin conditions - Any race and ethnicity (to be recorded) - Fitzpatrick skin type (to be recorded) - Women or men - Age: 22 to 65 years old - Subject with midface volume loss and contour deficiency ○ Administrative - Ability of giving consent for participation in the study - Agreement to adhere to the procedures and requirements of the study and to report to the institute on the day(s) and at the time(s) scheduled for the assessments.
Specific Exclusion Criteria:	
 ○ Skin conditions - History of allergy or hypersensitivity to lidocaine and/or injectable hyaluronic acid (HA) - Previous permanent or semi-permanent implant in proposed treatment area - Previous biodegradable tissue augmentation therapy in the proposed treatment area within 12 months prior to the baseline visit

Protocol Version 2:

This document contains confidential, proprietary information.

	
 - History of other facial treatment/procedure at the study area (midface) in the previous 6 months that would potentially interfere with study injections (e.g., facial surgery, oral surgery, resurfacing, mesotherapy, lipolytic injections, botulinum toxin injections)

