6. SELECTION AND DISPOSITION OF STUDY POPULATION

6.1 Number of Subjects

A minimum 15 subjects meeting inclusion/exclusion criteria listed below will be enrolled on the study to achieve 15 subjects who complete the study as planned.

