7.4 Method of Treatment Assignment

Before the start of the study, a randomization list will be prepared by the Sponsor utilizing a computer-generated software.

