8.1 Visits and Examinations

8.1.1. Screening/Baseline/Day 0 Visit (Visit 1)

1. Subjects will report to the testing clinical at D0 for baseline screening.
2. Prior to beginning of any study related activities, subjects will be informed about the purpose and nature of the study, the expected post-treatment events, and the potential risks involved with the treatments.
3. Subjects will be given an informed consent form, HIPAA form, photography release form, and Code of Conduct form to read.
4. Once subjects have completed reading, they will be interviewed to ensure their understanding of the aforementioned forms and be given the opportunity to ask any study related questions.
5. Subjects who agree to sign the aforementioned forms will be asked to complete a demographic information, medical history form, and concomitant medication form. Subjects declining to sign any of the forms will be dismissed from the study.
6. Subjects will be screened and qualified on the basis of the subject inclusion and exclusion criteria. Subjects failing to meet criteria will be dismissed from the study.
7. Subjects will have the below assessments by Investigator or a trained Clinic staff:
 - a. Clinical 2D photography by VISIA at neutral expression (3/4 left, front, 3/4 right), at closed-mouth smile (3/4 left, front, 3/4 right), and at open-mouth maximum smiling (3/4 left, front 3/4 right)
 - b. Clinical 3D photography by Vectra at neutral expression of full face
 - c. Ultrasound on each cheek at neutral expression and at maximum smiling (left and right). Note: ultrasound assessment will be performed at the same area of the injection.
8. Clinic staff or Investigator will assign the appropriate test treatment to each side of the face based on the predetermined computer-generated randomization.
9. Investigator will instruct the subjects on each treatment administration procedure and perform the treatments.
10. Investigator or Clinic staff will record the details of the administration, amount of each treatment used for each cheek and any subsequent adverse events (AEs) in the CRF.
11. Immediately post-injection, subjects will have the below assessment by Investigator:
 - a. Ultrasound on each cheek at neutral expression and at maximum smiling (left and right). Note: ultrasound assessment will be performed at the same area of the injection.
12. Subjects will be instructed on any standard care post-treatment and when to contact the Investigator in case of emerging AEs.

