10. STATISTICAL ANALYSIS

Data of completing subjects will be included for all statistical analyses. Descriptive statistical summary will be performed including N, mean, median, standard deviations, minimum, and maximum of values at all applicable time points and for both treatments.

For each study treatment, mean of the change from baseline will be estimated at applicable post-baseline time point. The null hypothesis, that the mean change from baseline is zero, will be tested using methods described in the Statistical Analysis Plan table.

The following will be calculated and reported for each evaluation parameter at applicable post-baseline time point:

$$\text{Percent mean change from baseline} = \frac{(\text{visit mean score} - \text{baseline mean score})}{\text{baseline mean score}} \times 100$$

$$\text{Percent of subjects improved/worsened} = \frac{(\text{number of subjects improved/worsened from baseline})}{\text{total number of subjects}} \times 100$$

Comparison between the study treatments will be made in terms of changes from baseline. The null hypothesis, that the mean change from baseline is equal between the 2 study treatments at post-baseline time point, will be tested using methods described in the Statistical Analysis Plan table.

Statistical Analysis Plan

Evaluation	Change from Baseline	Comparisons between study treatments	Notes/Interpretation
Ultrasound measurement ○ Aggregate size	Paired t-test; If normality fails, a Wilcoxon signed-rank test will be used.	Wilcoxon rank-sum test or sample t-test	N/A

Protocol Version 2:

This document contains confidential, proprietary information.

Volume change by 3D imaging analysis	Paired t-test; If normality fails, a Wilcoxon signed-rank test will be used.	Wilcoxon rank-sum test or sample t-test	A higher value reflects an improvement in skin volume.
--------------------------------------	------------------------------------------------------------------------------	-----------------------------------------	--------------------------------------------------------

Questionnaires will be tabulated, and the percentage of all response options will be reported for each question.

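### The between-filler test uses neither the pairing of cheeks nor the randomised side assignment, and no left/right balance is specified for the list

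*Combined protocol and SAP*

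**What the plan says.** The Synopsis describes a "Randomized, split-face, subject-blinded, comparative study". Step 8 of Section 8.1.1 says what is randomised: "Clinic staff or Investigator will assign the appropriate test treatment to each side of the face based on the predetermined computer-generated randomization". The method in Section 7.4 is one sentence, under which "a randomization list will be prepared by the Sponsor utilizing a computer-generated software". It gives no ratio, blocking or left/right restriction.

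Section 6.1 sets a minimum enrolment of 15 "to achieve 15 subjects who complete the study as planned". Section 10 adds: "Data of completing subjects will be included for all statistical analyses".

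For the between-filler comparison Section 10 states: "The null hypothesis, that the mean change from baseline is equal between the 2 study treatments at post-baseline time point, will be tested". For both aggregate size and 3D volume the table names "Wilcoxon rank-sum test or sample t-test". The rank-sum test is for independent samples, and the t-test entry does not mention pairing. Neither row has a term for side. Section 7.5 accepts that faces are naturally asymmetric and that the injected amount may differ between cheeks. It gives no size or direction for this.

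**The concern.** The design has two sequences: Contour left with Voluma right, and the reverse. If the change from baseline tends to be larger on one side whatever the filler, each subject's Contour-minus-Voluma difference is the filler effect plus that side effect in one sequence and minus it in the other. A test that ignores side then has two problems:

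- Near balance, the side effect goes into the error term, so the interval is too wide and power falls.
- At an uneven split, part of the side effect is also reported as a filler difference.

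Correcting the test to a paired one does not cure this, so the point is separate from the pairing problem in the same table cell. With 15 subjects, chance balance cannot be relied on. Because only completers are analysed, dropout can also disturb a list that began balanced.

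**Working it through.** **Inputs.** From the documents: n = 15 completers (Section 6.1), side as the randomised factor (Section 8.1.1) and change from baseline as the outcome (Section 10). The plan gives no alpha, power, effect size or SD, so it has no figure to reproduce. Assumed: two-sided 5%, normal errors, s = 1, and L = 0 to 1 s. L is the left-minus-right difference in change with the same filler on both sides.

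**Model.** D = filler effect + L if Contour is on the left, and filler effect − L if it is on the right. Let nL and nR be the numbers of subjects with Contour left and right.

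**Chance of each split under simple randomisation.** P(11:4 or worse) = 2 × (1 + 15 + 105 + 455 + 1365)/32768 = 3882/32768 = 11.8%. Adding the 10:5 term, 2 × (1941 + 3003)/32768 = 30.2%. P(8:7) = 39.3%.

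**Share credited to a filler.** The mean of D shifts by L(nL − nR)/n: 1/15 = 0.07L at 8:7, 5/15 = 0.33L at 10:5 and 7/15 = 0.47L at 11:4.

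**Interval width at 8:7.** The expected variance of D is s² + L²[n − (nL − nR)²/n]/(n − 1) = s² + 1.067L². With t = 2.145 (14 df), the half-width is 2.145 × √1.267/√15 = 0.62s at L = 0.5s and 2.145 × √2.067/√15 = 0.80s at L = s. The average sample SD is slightly below the root of the expected variance, so the simulated mean half-widths are 0.61s and 0.78s to 0.79s. With side as a factor the simulated value is 0.55s at any L.

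**Type I error of a paired t-test without side (simulation, agreeing to about 0.2 points between runs).**

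| Split | Probability | Credited | L = 0.25s | L = 0.5s | L = s |
|---|---|---|---|---|---|
| 8:7 | 39% | 0.07L | 4.4% | 3.1% | 0.8% |
| 9:6 | 31% | 0.20L | 4.8% | 4.1% | 2.3% |
| 10:5 | 18% | 0.33L | 5.4% | 6.2% | 6.7% |
| 11:4 | 8% | 0.47L | 6.5% | 9.8% | 17.1% |

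With side as a factor, type I error is about 5% at every split and L tried.

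**Averaged over simple randomisation.** The paired test without side holds 4.9% to 5.0%. Its power at a filler effect of 0.8s is 0.82, 0.73 and 0.52 for L = 0, 0.5s and s. With side as a factor, power is about 0.79 for any L.

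**If the table is read as an unpaired t-test.** Averaged over simple randomisation, type I error at L = 0, 0.5s and s is 0.8%, 1.4% and 3.1% if the two cheeks correlate at 0.5, and 5.0%, 6.2% and 8.8% if they do not correlate. At correlation 0.5 and L = 0, power at 0.8s is 0.58, against 0.82 paired.

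**Cost of adjusting when L = 0.** The standard error is multiplied by √[(1/nL + 1/nR)/4] × √15, which is 1.002 at 8:7, 1.061 at 10:5 and 1.131 at 11:4. Multiplying by 2.160/2.145 = 1.007 for the lost degree of freedom, the interval is about 1%, 7% and 14% wider.

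**The case against.** A reader might infer that the list is unbalanced. The documents do not say so. Section 7.4 is silent, and a blocked list is compatible with it. What can be said is that no balance is specified.

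A reader might also take the natural asymmetry in Section 7.5 as evidence of a side effect. It is weak evidence. Fixed baseline asymmetry cancels in a change score, and asymmetry without a consistent direction is already part of s. Only a consistent left-right difference in the change counts, for example from injection or probe placement. Nothing in the documents shows one, and L = s is the extreme of the assumed range.

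Nor is the trial biased on average: over simple-randomisation lists the expected shift is zero and the paired test keeps its level. About 70% of such lists (39% + 31%) give a conservative test, and 10:5 is only mildly inflated. The 10% to 17% figures belong to a split with 8% probability. The adjustment also has a price at uneven splits when L = 0, with power 0.72 at 11:4 against 0.82 unadjusted.

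All of this stands, and it limits the claim. It does not remove it. The trial will have one known split, and its readers face the error conditional on that split. The power loss when L is not zero does not average out.

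**Conclusion.** The point holds in a limited form. The plan randomises side, specifies no balance on it, and compares fillers with tests that use neither pairing nor side. If a consistent left-right difference in change exists, a paired test without side is conservative near 8:7 and, at 11:4, has 10% to 17% type I error for L between 0.5s and s. Power is lost on average. If L = 0, ignoring side does no harm, and the pairing problem in the same cell remains.

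It would go too far to say that the intervals must be wrong in one direction or the other. That requires L to be non-zero, and its size here is assumed throughout. The tabulated errors are for a paired t-test, which the table does not clearly list. The case for change is that the better analysis needs no new data and protects the level at any split.

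**What to change.** **Section 10.** Replace the between-filler entry in both rows. Analyse each subject's Contour-minus-Voluma change with side assignment as a factor, so that the filler effect is the average of the two sequence means. Report it with a 95% CI at each time point.

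If normality fails, use the rank-based two-sequence version: compare the left-minus-right differences in change between the two side-assignment groups with a rank-sum test. The side effect is common to both groups and cancels, and the location difference is twice the filler effect. The rank-sum test already named can therefore stay, applied to these differences.

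**Section 7.4.** State that the list is generated in small permuted blocks balanced on side, so that near-balance survives enrolment beyond 15 or dropout. A list fixed at 8:7 for exactly 15 subjects would not do this. If the list already exists, the analysis change alone still keeps the level at about 5%.

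The order of steps in Section 8.1.1 needs no change, because assignment (step 8) already follows the baseline assessments (step 7).

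**Cost.** Compared with a paired t-test, one degree of freedom (critical value 2.160 instead of 2.145) and no new data. If L = 0 the interval is about 1% wider at 8:7 but 14% wider at 11:4, which is why the list should be balanced as well as the analysis adjusted.

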5. STUDY OBJECTIVE AND CLINICAL HYPOTHESIS

5.1 Study Objective

To assess and compare tissue aggregation and visualization of two Hyaluronic Acid fillers via ultrasound.

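### For aggregate size and 3D volume, the fillers are compared only by an independent-sample test of equal mean change, so the precision of the within-subject difference cannot be recovered from the planned output

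*Combined protocol and SAP*

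**What the plan says.** The objective in Section 5.1 is comparative: "To assess and compare tissue aggregation and visualization of two Hyaluronic Acid fillers via ultrasound". The Synopsis describes the design as "Randomized, split-face, subject-blinded, comparative study", so both fillers are placed in the same person. Section 6.1 says that enough subjects "will be enrolled on the study to achieve 15 subjects who complete the study as planned". It gives no alpha, power, target difference or SD.

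Section 10 contains the whole statistical plan. Its outputs within each filler are these:
- "For each study treatment, mean of the change from baseline will be estimated at applicable post-baseline time point".
- "Descriptive statistical summary will be performed including N, mean, median, standard deviations, minimum, and maximum of values", by time point and treatment.
- The percentage change in the mean, and the share of subjects who improved or worsened.

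Between fillers, Section 10 gives only a null hypothesis, "that the mean change from baseline is equal between the 2 study treatments at post-baseline time point". The table names the same method for aggregate size and for 3D volume: "Wilcoxon rank-sum test or sample t-test". The adjacent column, for change from baseline within a filler, names a paired t-test with a signed-rank fallback. Neither the Synopsis nor Section 10 plans a within-subject difference between fillers, its SD, or an interval for it.

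**The concern.** In a split-face trial, the quantity that answers the objective is the difference between a subject's two cheeks. Its standard error depends on how strongly the cheeks are correlated. The plan summarises each filler separately and then tests the two as if they came from different people, so the correlation appears in none of its outputs.

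What is at stake is how the main comparison can be interpreted. With 15 subjects and no stated power, a reader of a non-significant p-value needs to know which differences the data still allow. The planned output does not say. The data themselves are unaffected, and the missing information can be computed from what is already collected.

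**Working it through.** There is no sample-size or precision figure in the documents to reproduce, so the check computes precision at the stated n.

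**Inputs.** From the documents: n = 15 completers (Section 6.1), both cheeks treated, hence 15 pairs. Assumed, because the documents give none: two-sided 0.05, equal SD of change for the two fillers (call it SD), and a between-cheek correlation ρ of 0 to 0.9. SD_d is the SD of the paired difference.

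**1. What can be recovered.** For completers with both cheeks measured, the mean paired difference equals the difference of the two planned mean changes. For its standard error, Var(difference) = SD₁² + SD₂² − 2ρ·SD₁·SD₂. The per-filler summaries do not give ρ. An independent-sample t statistic is the difference divided by pooled SD × √(2/n), so working back from its p-value returns the pooled SD and not ρ. A rank-sum p-value does not supply ρ either. By contrast, a paired t-test with an exact p-value would give the standard error as the difference divided by t.

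**2. Paired half-width.** t(0.975, 14)/√15 = 2.145/3.873 = 0.554 SD_d.

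**3. The same in per-filler SD units.** SD_d = SD × √(2(1−ρ)), and the half-width is 0.554 × √(2(1−ρ)).

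**4. Nominal half-width of the unpaired t-test.** t(0.975, 28) × √(2/15) = 2.048 × 0.365 = 0.748 SD, with no dependence on ρ.

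| Assumed ρ | SD_d / SD | Paired half-width (SD) | Unpaired nominal half-width (SD) |
|---|---|---|---|
| 0 | 1.414 | 0.783 | 0.748 |
| 0.3 | 1.183 | 0.655 | 0.748 |
| 0.5 | 1.000 | 0.554 | 0.748 |
| 0.7 | 0.775 | 0.429 | 0.748 |
| 0.9 | 0.447 | 0.248 | 0.748 |

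The two half-widths are equal when 1−ρ = (0.748/0.783)² ≈ 0.91, that is at ρ ≈ 0.09. Above that, the unpaired figure is too wide.

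**5. Consequence for the test.** Simulation with normal data, 15 pairs and 40,000 runs per setting:

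| Assumed ρ | Type I error, unpaired t | Type I error, paired t | Power at 0.5 SD, unpaired t | Power at 0.5 SD, paired t |
|---|---|---|---|---|
| 0 | 4.9% | 5.0% | 26% | 25% |
| 0.5 | 0.8% | 4.9% | 20% | 44% |
| 0.7 | 0.1% | 4.9% | 15% | 64% |

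**6. Power of a correctly paired test.** From the noncentral t with 14 df, power is 19% at a true difference of 0.3 SD_d, 44% at 0.5 and 82% at 0.8. A paired result just short of significance would have an interval from about 0 to 2 × 0.554 ≈ 1.1 SD_d. A p-value alone does not show that.

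**The case against.** Several points on the other side are sound.

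- *The plan does yield a difference.* A reader might infer that no between-filler estimate exists and that the comparison cannot be read at all. Section 10 does not support that: it estimates both mean changes in completers, and subtraction gives the paired mean difference if both cheeks are measured. Only the precision is lost.
- *The trouble is mainly the unpaired test.* Much of it is. A paired t-test with an exact p-value would let a reader rebuild the interval. Even so, changing the test alone would leave the estimate and interval uncommitted, and the rank-based route would still have neither. The two corrections belong together.
- *The t-test wording is loose.* The table does not say which kind of t-test is meant, and a one-sample test on the differences would be paired. The rank-sum test is unambiguously for independent samples, however, and the adjacent column says paired where it means paired. Independent-sample is the natural reading.
- *No passage plans to claim equality.* A reader might suppose that a non-significant test would be reported as equal behaviour. The documents set no margin and state no such conclusion, and Section 5.2 expects the effects to differ. That misreading remains only a risk.
- *Unstated power is not low power.* This stands. A paired test has 82% power at 0.8 SD_d, so it cannot be said in general that non-significance is likely.

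**Conclusion.** The point holds as a fault in the choice and reporting of the between-filler analysis. For the two tested outcomes, the plan pairs a split-face design with independent-sample tests and commits to no interval or paired-difference SD, so the precision of its central comparison cannot be recovered from its output.

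The size depends on the unknown correlation. The paired half-width is 0.78 SD at ρ = 0 and 0.55 SD at ρ = 0.5, a ratio of 1.4. It reaches 0.25 SD, about threefold narrower than at zero, only at an assumed ρ of 0.9, for which the documents offer no basis. The threefold figure is the end of a range and not a finding about this trial. If the cheeks are nearly uncorrelated, the unpaired nominal width is close to the paired one. The figures also assume normal changes, equal SDs, two-sided 0.05 and a full 15 pairs.

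The change should be made, because it gives a better answer to the stated objective from data already collected. It does not call for more subjects or a power claim.

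**What to change.** Amend Section 10 for aggregate size and 3D volume as follows.

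1. Make the main between-filler result the mean within-subject difference in change from the pre-injection baseline (Restylane Contour cheek minus Juvéderm Voluma cheek), with its SD and paired 95% confidence interval.
2. If the paired differences fail the normality check, report the Hodges-Lehmann estimate with its interval.
3. Replace the rank-sum or independent-sample t-test with the matching paired t-test or Wilcoxon signed-rank test, as a secondary p-value. Otherwise a paired interval would stand beside an unpaired p-value, and the two could disagree.
4. Give the results at each post-injection time point and, for ultrasound, for each expression. Under Sections 9.2 and 9.3 that is 3 time points × 2 expressions = 6 for aggregate size and 2 time points for 3D volume.
5. State that non-significant results will be interpreted through the interval.

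The cost is SAP wording and some added table columns. No new data, visits or subjects are needed.

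### Section 10 states nulls about means but leaves the test open: a normality check can swap the within-filler test, and the between-filler comparison lists two unpaired tests with no rule, although every subject receives both fillers

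*Combined protocol and SAP*

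**What the plan says.** Section 10 gives two nulls, both about means. Within each filler: "The null hypothesis, that the mean change from baseline is zero, will be tested using methods described in the Statistical Analysis Plan table". Between fillers: "The null hypothesis, that the mean change from baseline is equal between the 2 study treatments at post-baseline time point". The summaries that go with them include mean change and percent mean change.

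The Statistical Analysis Plan table then sets the tests, with the same entries for ultrasound aggregate size and 3D volume:

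- Change from baseline: "Paired t-test; If normality fails, a Wilcoxon signed-rank test will be used".
- Comparison of fillers: "Wilcoxon rank-sum test or sample t-test".

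No normality test, cut-off, significance level or expected distribution is given. The comparison column has no normality condition and no other rule for choosing. I read its t-test as the two-sample one, the natural partner of the rank-sum test; the table does not say.

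On numbers, Section 6.1 enrols a minimum of 15 "to achieve 15 subjects who complete the study as planned", and Section 10 adds "Data of completing subjects will be included for all statistical analyses". Under Section 8.1.1 the fillers are assigned to the two sides of each face by randomisation.

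**The concern.** The within-filler rule chooses its test from the same 15 or so values that it then tests. If the check fails, the signed-rank test is used. That test addresses symmetry about zero, so with asymmetric changes it can reject when the mean change is exactly zero. The p-value printed beside a mean may then not refer to that mean. If the check passes, the changes may still be skewed, because 15 values often cannot show it.

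The between-filler comparison is the objective in Section 5.1. Each subject supplies one cheek per filler, so the two changes are paired by design. Both listed tests, as I read them, treat the cheeks as 30 independent faces. The plan also does not say which of the two will be reported.

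**Working it through.** The plan states no error rate or power, so there is no figure of its own to reproduce.

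**Inputs.** From the documents: n = 15 (Section 6.1), mean nulls and test rules (Section 10). Assumed, because the documents are silent: Shapiro-Wilk at 5%, two-sided alpha of 5%, and the shape of the changes.

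**Step 1: within filler.** Simulation with 20,000 runs per shape, each centred so that the true mean change is 0. Rule: paired t-test if Shapiro-Wilk p is at least 0.05, otherwise exact signed-rank. Rejection rates:

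| Shape | Paired t alone | Signed-rank alone | Plan's rule | Added by switch (points) |
|---|---|---|---|---|
| Normal | 4.9% | 4.7% | 5.0% | 0.1 |
| Laplace (symmetric) | 4.2% | 4.4% | 4.4% | 0.2 |
| t, 3 df (symmetric) | 4.0% | 4.7% | 4.7% | 0.7 |
| Gamma, skew 0.71 | 5.7% | 5.8% | 6.0% | 0.3 |
| Lognormal, log-SD 0.25 | 5.3% | 5.4% | 5.7% | 0.4 |
| Gamma, skew 1 | 5.9% | 6.3% | 6.6% | 0.7 |
| Lognormal, log-SD 0.5 | 7.1% | 8.3% | 8.4% | 1.3 |
| Gamma, skew 1.4 | 7.2% | 8.2% | 8.5% | 1.3 |
| Exponential | 9.0% | 11.0% | 11.3% | 2.3 |
| Lognormal, log-SD 0.75 | 10.1% | 13.0% | 13.2% | 3.1 |
| Gamma, skew 2.8 | 11.9% | 17.1% | 17.2% | 5.3 |
| Lognormal, log-SD 1.0 | 14.6% | 20.0% | 20.2% | 5.6 |

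The excess over 5% splits as follows. For the exponential, 11.3 − 5 = 6.3 points, of which 9.0 − 5 = 4.0 are already there with the t-test alone (63%). For log-SD 1.0, 9.6 of 15.2 points (63%). Most of the excess in the moderate-to-strong range therefore comes from testing a mean on 15 skewed values, and the smaller part from the switch.

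Nor does the check screen skewed data well. At log-SD 0.5, exponential and log-SD 1.0 it passes 1 − 0.393 = 61%, 1 − 0.675 = 33% and 1 − 0.825 = 18% of samples. The t-test used after a pass then errs 9.5%, 13.1% and 34.6% of the time.

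**Step 2: between fillers.** Let σ be the SD of change in a cheek and ρ the correlation between a subject's two cheeks (neither is in the documents). The mean difference has variance 2σ²(1 − ρ)/15, but a two-sample t-test uses 2σ²/15. With roughly normal changes, the observed difference needed for p < 0.05 is:

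- Two-sample t (28 df): 2.048 × √(2/15) σ = 0.748σ, whatever ρ is.
- Paired t (14 df): 2.145 × √(2(1 − ρ)/15) σ = 0.783σ at ρ = 0, 0.554σ at ρ = 0.5, 0.429σ at ρ = 0.7.

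The ratio of unpaired to paired is 0.96, 1.35 and 1.74. Pairing costs about 5% in the threshold if the cheeks are unrelated and gains a lot if they are not.

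Simulated false-positive rates with equal means and the same lognormal shape agree (ρ here is on the log scale):

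| Log-SD, ρ | Two-sample t | Rank-sum | Paired t |
|---|---|---|---|
| 0.5, 0 | 4.8% | 4.5% | 4.7% |
| 0.5, 0.5 | 0.9% | 0.9% | 4.6% |
| 0.5, 0.8 | 0.0% | 0.0% | 4.6% |
| 1.0, 0 | 3.7% | 4.3% | 3.6% |
| 1.0, 0.5 | 0.7% | 0.7% | 3.0% |
| 1.0, 0.8 | 0.0% | 0.1% | 3.0% |

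**Step 3: does the choice of test matter for the mean null?** With equal means but different shapes for the two fillers and ρ = 0, the rank-sum test rejects 22.5% of the time (log-SD 0.5 against 1.0) and 38.1% (0.25 against 1.0). The two-sample t-test rejects 9.2% and 13.9%. The two listed tests can therefore give quite different answers about the same stated null.

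**The case against.** - **The switch as the cause.** A reader might infer that the switch itself drives the error rate to 9-20%. The documents do not support that: they give no distribution, alpha or normality test, and the t-test without any switch already gives 7-15% under the same moderate to strong skew.
- **The simulated null may rarely arise.** For aggregate size, a pre-injection baseline should show no study filler, and Section 6.4 excludes recent or permanent fillers. Changes would then be zero or positive, and a skewed change with mean exactly zero could not occur. It could occur if the immediate post-injection scan, which Section 9.3 also lists under baseline, is the reference. For 3D volume, Section 7.5 treats subjects to optimal correction, so a zero mean at week 4 is implausible. This stands, and it lowers the practical weight of the within-filler error rates. It does not remove the mismatch between the test and the reported mean.
- **The switch has a benefit.** In one heavy-tailed simulation, at an assumed effect size, it had 86% power against 81% for the t-test. That stands as a cost of the fix.
- **The open choice as a route to false positives.** A reader might infer that choosing the better of two between-filler p-values inflates error. With the same shape in both fillers, neither listed test exceeds 5%, and positive correlation makes both strongly conservative. The clearer loss is sensitivity, plus a test that is not fixed in advance.
- **Sign-flip as an assumption-free test of the mean.** It is not one. Side randomisation justifies it for no difference in any subject. Against the mean null alone, with asymmetric differences, it erred 8.3% (exponential) and 14.1% (log-SD 1.0), about the same as the t-test.
- **The study is small, with no stated alpha or primary endpoint.** True, but the between-filler test still serves the stated objective.

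**Conclusion.** The point holds in two parts of unequal weight.

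The between-filler part is the more important. The plan should fix one paired test in advance, and this follows from the design alone. How much it gains depends on ρ: for ρ of 0.5-0.7 the unpaired tests run at roughly 0.1-1% instead of 5% and need an observed difference about 1.35 to 1.74 times as large. At ρ = 0 there is no gain and a small cost.

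The within-filler part is a modest defect of specification. Given the assumed Shapiro-Wilk check and two-sided 5%, the rule's error for the mean null is about 5% with symmetric changes, 6-7% with mild skew and 8-20% with moderate to strong skew. The switch accounts for only about 0.3 to 6 points of that across the skewed cases. How skewed these changes will be is unknown.

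**What to change.** **Comparison column.** Replace the two listed tests with one named test on the within-subject difference between fillers in change from baseline, for each parameter and visit. Two choices are sound, and the SAP should commit to one:

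- the paired t-test with a 95% confidence interval for the mean difference, which matches the null as written; or
- the exact sign-flip test, described as a test of no difference between fillers. It must use the sign patterns that the randomisation list allows: 2^15 = 32,768 if sides are assigned independently, fewer if the list is balanced or blocked. Section 7.4 does not say which.

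**Change-from-baseline column.** Make the paired t-test with a 95% confidence interval the single analysis of mean change. Report the signed-rank test with its Hodges-Lehmann estimate every time as a sensitivity analysis, and drop the switch on a normality check. A bootstrap-t interval is optional: it came closer to 5% in the skewed cases (5.3-8.1%), but at log-SD 1.0 its median width was 1.26 times that of the t interval.

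**Also** state alpha and sidedness.

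**Cost.** SAP wording and a few lines of code, with no change to visits or data. Some power is lost if changes are heavy-tailed, and the t-test remains above 5% under strong skew, which the report should acknowledge.
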